Furthering our understanding of the psychosocial sequelae of IBD in children and young adults is particularly important in light of evidence suggesting that symptoms of anxiety and depression may decrease adherence to treatment, thus impacting on longer term disease outcomes,(6) and has been emphasized in a recent call to action issued within gastroenterology to improve understanding and early identification of comorbidities associated with IBD.(10)

To the best of our knowledge, there have not been any large population-based studies assessing the association between psychosocial comorbidities in IBD in

children and young adults and disease related outcomes. The aim of this study is therefore to fill this data gap, and to examine the following objectives.

Such new insights will be valuable for clinicians in optimising patient care for IBD patients; allowing early interventions to be targeted to those most at risk, and potentially preventing the development of more serious mental health problems such as depression; linked to difficulties with medication adherence, and anxiety; which may exacerbate future disease activity.(7, 10)

Ultimately, we anticipate that these data will be useful in understanding the potential cycle and interrelationship between IBD and mental health in children and young adults.

Objectives: Stream 1 – Incidence of mental health conditions

Primary Objectives

- Compare the risk and cumulative incidence of mental health conditions in children and young adults with IBD compared to matched population controls in the primary care setting, stratified by IBD type

Secondary Objectives

- Determine severity of mental health conditions in those with and without IBD (e.g. evidence of self-harm, suicide attempt, behavioural disorders)

Objectives: Stream 2 – Impacts of mental health conditions

Primary Objective:

- Determine the association of mental health conditions in children and young adults with IBD on quality-of-life indicators

Secondary Objectives:

- Compare IBD severity/disease markers in children and young adults with IBD with and without mental health illness

- Compare healthcare resource utilisation in children and young adults with IBD with and without mental health illness

Methods

The study protocol was specified a priori and registered with ClinicalTrials.gov (Study identifier: NCT05206734).

Data source

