To evaluate the magnitude of potential bias from including, as matched controls, people who are registered with GP practices but who do not attend their practice, we also repeated the primary analysis including only controls with a least one primary care consultation in the year preceding their index date.

All statistical analyses were performed using R statistical package software version 3.4.1. The study was conducted in line with the RECORD (Reporting of studies conducted using observational routinely collected data) guidelines.(13)

Stream 2:

Stream 2: Study design

The proposed study will use the retrospectively collected data of all eligible patients within the database at the date of data extraction. Within this primary care cohort, all patients with IBD will be identified using diagnostic codes and prescription records. A diagnostic algorithm will be developed to facilitate robust case identification of IBD and IBD subtypes as well as mental health outcomes.

Stream 2: Study cohort

The eligible IBD cases will comprise all prevalent cases of IBD aged under 25 at 01/01/2015 (index date) comprising of the three main subtypes; ulcerative colitis (UC), Crohn's disease (CD) and IBD unclassified (IBDU), excluding microscopic colitis, radiation induced enterocolitis and drug-induced enterocolitis. We will extract sociodemographic details for all individuals. Sociodemographic data will comprise by age group, age at diagnosis, sex, ethnicity, and socioeconomic status. Ethnicity will be categorised as follows to be consistent with the UK official census categories: White, Asian, Black African/Caribbean, Mixed, and Other. The index of multiple deprivation (IMD) will be used as a measure of socioeconomic status. This is derived from patient postcode at the point of data extraction.

We will identify comorbid psychological condition groups in all people with PIBD. These will comprise 3 composite phenotypes; anxiety/panic disorders, major depression or depressive episodes, and other psychological conditions. Other psychological conditions will be a composite of; eating disorders, body image disorder, attention-deficit disorder (ADHD), behavioural disorders, adjustment disorder, acute stress disorder, schizophrenia, bipolar disorder and post-traumatic stress disorder (PTSD). Where numbers are sufficient, subgroups of the broad 'other psychological conditions' composite may be examined.

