At the index date, we will define groups in the IBD case population based on mental health phenotype, including a comparator group without mental health comorbidity at the index date, and compare the sociodemographic characteristics of these groups.

Stream 2: Follow-up

We will then describe incidence of each study outcome in the five years after the index date for each group, and the relative incidence of each outcome in those with and without mental health comorbidity.

Stream 2: Study outcomes

These will comprise the following.

Quality of life indicators:

Affective symptoms (depression, low mood, deliberate self-harm, suicidal ideation or parasuicide), IBD symptoms, absence from school, absence from work, unemployment, substance abuse, and sleep problems. IBD symptoms will comprise; abdominal pain, discomforts or bloating, diarrhoea, weight loss, growth retardation and tiredness/fatigue. (See Appendix 1 – Table s1 for Read Codes and SNOMED codes).

IBD severity indicators:

Medication use, surgical intervention, nutritional supplement use, and markers of nutritional status. Surgical intervention will comprise any abdominal surgery, and stoma formation (as a separate outcome). Medication use will comprise use of: rectal 5-aminosalicylic acid (5-ASA), oral 5-ASA, rectal steroids, oral steroids, antimetabolites, tumour necrosis factor inhibitors (TNFi) and other biologic therapies. The latter of these groups may not be well captured in primary care and if so this will be reported in the limitations section of the final study manuscript. Nutritional supplements will comprise the five most prescribed nutritional supplements: Modulen, Fortisip, Ensure, Osmolite, and Neocate. Nutritional markers will comprise; being underweight (under the 5th centile of weight for height or BMI < 18.5 kg/m² after age 18) and growth retardation related codes. (See Appendix 1 – Table s2 for Read Codes and SNOMED codes).

Healthcare resource utilisation:

Primary care attendances and hospital admissions. Hospital admissions will be separated into general admissions (including those for IBD) and psychiatric admissions. (See Appendix 1 – Table s2 for Read Codes and SNOMED codes).

Stream 2: Statistical methods

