Read CTV3 Code	Term ID	Description
SNOMED Code	Term ID	Description

sTable 2.2 Algorithms used to identify anxiety episodes, depression episodes, and recurrent major depression. Expressions in capitals equate to Boolean expressions. *More than 1 year ago. SSRIs = selective serotonin reuptake inhibitors, TCA = tricyclic antidepressants, MAOI = monoamine oxidase inhibitors, CBT = cognitive behavioural therapy.

Clinical entity	Definition
Anxiety	Any coded anxiety episode AND concurrent treatment for anxiety
Depressive episode	Any coded depressive episode AND concurrent treatment for depression
Recurrent depressive disorder	(Any historical code* for a depressive episode AND current treatment for depression) OR Any code for recurrent depressive disorder
Anxiety treatments	SSRIs, anxiolytics, counselling, CBT, and psychotherapy
Depression treatments	SSRIs, TCAs, MAOIs, counselling, CBT, and psychotherapy

sTable 2.3 WHO International Statistical Classification of Diseases (ICD-10) for mental health conditions

Clinical entity	ICD 10 code	Definition
Depressive episode	F32	Any coded depressive episode AND concurrent treatment for depression
Recurrent depressive disorder	F33	(Any historical code* for a depressive episode AND current treatment for depression) OR Any code for recurrent depressive disorder
Depression treatments	NA	SSRIs, TCAs, MAOIs, counselling, CBT, and psychotherapy
Anxiety	F41	Any coded anxiety episode AND concurrent treatment for anxiety
Anxiety treatments	NA	SSRIs, anxiolytics, counselling, CBT, and psychotherapy
Self-harm	X60-X84	Any diagnostic or indicative code for any form of self-harm, including suicide attempt
Eating disorders	F50	Any diagnostic or indicative code for eating disorders

Body image disorders	F45.2	Any diagnostic or indicative code for body image / dysmorphic disorder (excluding hypochondriacal disorders not associated with body image)
Attention-deficit disorders	F90.0	Any diagnostic or indicative code for disturbance of activity and attention
Behavioural disorders	F91 F92	Any diagnostic or indicative code for conduct disorders
Adjustment disorders	F43.2	Any diagnostic or indicative code for adjustment disorders
Acute stress disorders	F43.0	Any diagnostic or indicative code for acute stress disorders
Post-traumatic stress disorder	F43.1	Any diagnostic or indicative code for Post-traumatic stress disorder

Appendix 3

sTable 3.1 Read and SNOMED codes to be used to identify quality of life

Depressive episode		

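### Stream 2: four weight-related outcomes count as IBD severity or IBD symptoms whatever their cause, so contrasts whose exposed group includes eating disorders partly measure the eating disorder

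*Combined protocol and SAP*

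**What the plan says.** **Exposure.** Under Stream 2: Study cohort, IBD patients are grouped at the index date into anxiety/panic, depression and a third phenotype: "Other psychological conditions will be a composite of; eating disorders, body image disorder, attention-deficit disorder (ADHD"), followed by six further conditions, nine in all. sTable 2.3 defines the eating-disorder component (F50) as "Any diagnostic or indicative code for eating disorders", with no condition on weight or current activity. The comparator is IBD patients with no mental health comorbidity at index.

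**Outcomes.** Under Stream 2: Study outcomes, the severity indicators are "Medication use, surgical intervention, nutritional supplement use, and markers of nutritional status". The nutritional items are then spelled out:

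- "Nutritional markers will comprise; being underweight (under the 5th centile of weight for height", or a BMI below 18.5 kg/m² after age 18), together with growth-retardation codes.
- "Nutritional supplements will comprise the five most prescribed nutritional supplements: Modulen, Fortisip, Ensure, Osmolite, and Neocate".

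Among the quality-of-life indicators, "IBD symptoms will comprise; abdominal pain, discomforts or bloating, diarrhoea, weight loss, growth retardation and tiredness/fatigue".

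**Use.** The severity indicators serve the Stream 2 secondary objective: "Compare IBD severity/disease markers in children and young adults with IBD with and without mental health illness". The quality-of-life indicators serve the Stream 2 primary objective.

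**Safeguards.** Stream 2: Statistical methods adjusts for age, gender, socioeconomic status, ethnicity and a list of physical conditions. Stream 2: Study cohort adds: "Where numbers are sufficient, subgroups of the broad 'other psychological conditions' composite may be examined". The closing paragraph of Stream 2: Statistical methods also foresees reporting by mental health condition group, again only if numbers allow.

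**The concern.** A restrictive eating disorder can produce low weight, weight loss and supplement prescriptions by itself. A patient whose bowel disease is quiet but who has such a disorder would score on underweight, weight loss and supplement use, and the plan would record this as IBD severity or IBD symptoms. That patient sits in the exposed group by definition. For these outcomes the exposure therefore feeds the outcome directly, and the error runs in one direction, towards the association that the objective looks for.

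At stake is how a raised ratio for these outcomes in the 'other' phenotype is read. It could be reported as mental illness going with more severe IBD when part or all of it reflects the eating disorder. Weight loss and growth retardation carry the same problem into the quality-of-life set.

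**Working it through.** **1. Does anything in the plan break the link?** Setting the sections side by side:

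- Outcome definitions: no requirement that low weight, a supplement, weight loss or a growth code be due to IBD.
- Model covariates: no eating disorder, no baseline weight or BMI, no baseline IBD severity.
- Sensitivity analyses: the only one described belongs to Stream 1 and concerns controls who do not attend their practice.
- Subgroups: both statements are conditional on numbers, and neither changes the main contrast.

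So the link stands in the main analysis.

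**2. Which outcomes are reached?** Underweight, supplement use, weight loss and growth-retardation codes. The seven medication classes, abdominal surgery and stoma formation are not reached by this route.

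**3. How large could it be?** The plan states no group sizes, event rates or effect sizes for this contrast, so there is no figure to reproduce. Suppose there is no true difference in IBD severity. Let f be the share of the 'other' group with an eating disorder, and R the ratio of the outcome rate in those patients to the comparator rate, due to the eating disorder alone. Both are assumptions. With equal follow-up,

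induced ratio = f·R + (1 − f)·1 = 1 + f·(R − 1).

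| f | R = 2 | R = 3 | R = 5 | R = 10 |
|---|---|---|---|---|
| 2% | 1.02 | 1.04 | 1.08 | 1.18 |
| 5% | 1.05 | 1.10 | 1.20 | 1.45 |
| 10% | 1.10 | 1.20 | 1.40 | 1.90 |
| 20% | 1.20 | 1.40 | 1.80 | 2.80 |
| 30% | 1.30 | 1.60 | 2.20 | 3.70 |

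**4. The same check on the risk scale.** Assume a five-year underweight risk of 8% in comparators and in 'other' patients without an eating disorder, and 30% to 50% in those with one. Then R = 0.30/0.08 = 3.75 to 0.50/0.08 = 6.25.

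- f = 5%: 1 + 0.05 × 2.75 = 1.14 to 1 + 0.05 × 5.25 = 1.26.
- f = 10%: 1 + 0.10 × 2.75 = 1.28 to 1 + 0.10 × 5.25 = 1.53.

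Taking R from 3 to 6.25 across both sets of assumptions gives about 1.1 to 1.3 at a 5% share and 1.2 to 1.5 at 10%.

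**5. Pooled contrast.** If the 'other' group is a fraction g of all patients with mental illness, the share becomes g·f and the induced ratio 1 + g·f·(R − 1). The direction is the same and the size smaller.

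**6. Would it reach nominal significance?** Assume 200 exposed, 1000 comparators and a comparator risk p0 = 10%, with p1 = p0 × induced ratio. The normal approximation is Φ[(p1 − p0 − 1.96·SE0)/SE1], where SE0 uses the pooled risk and SE1 the separate risks. The chance of a false result in the 'worse' direction, against 2.5% without the overlap, is:

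- f = 5%, R = 3 (p1 = 0.11): about 7%.
- f = 10%, R = 5 (p1 = 0.14): about 40%.
- f = 20%, R = 5 (p1 = 0.18): about 87%.

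**The case against.** **The size is unknown and may be trivial.** Eating disorders are one of nine conditions in the composite, and any F50 code qualifies, not only restrictive disease. At a 2% share and R of 2 to 3, the induced ratio is 1.02 to 1.04. This stands: the direction can be read from the definitions, the importance cannot.

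**A reader might infer that the 'other' phenotype would be shown to have worse IBD overall.** The documents do not support that. There is no overall severity score, incidence is described outcome by outcome, and stoma is a separate outcome. Underweight or supplement use raised on its own, with surgery and IBD drugs unchanged, would be visible to a careful reader. In the quality-of-life set, weight loss and growth retardation are two items under one of seven indicators. sTable 3.1 gives the symptoms separate headings, although the plan does not say whether they are analysed singly or together.

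**A reader might extend the point to ADHD, which is in the same composite.** The documents say nothing about ADHD treatment or its effect on weight or growth, so that extension has no basis here.

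**The plan already foresees subgroups.** It does, in two places. Both depend on numbers, neither names eating disorders, and the main estimate stays mixed either way.

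**Excluding these patients discards real signal.** The Background names growth failure as a consideration in paediatric IBD, and low weight in someone with both conditions may come from either. This also stands, and is why the all-inclusive estimate should be kept. A limitation statement alone would be cheaper, but would leave no estimate free of the overlap.

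**Conclusion.** The point holds for four outcomes only: underweight, nutritional supplement use, weight loss and growth-retardation codes. For these, the 'other' contrast and any pooled with/without contrast are biased towards worse IBD if the plan is followed as written. The conclusion rests on the plan's own definitions plus one premise from general clinical understanding, that eating disorders can themselves cause these outcomes.

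The size rests entirely on assumed f and R. It is negligible at a 2% share with a modest R, moderate at 5% to 10%, and large only if eating disorders form a substantial part of the composite. The documents do not give that share, so they neither show a material bias nor rule one out. This is an inexpensive improvement to the specification; it does not undermine Stream 2 as a whole.

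**What to change.** Add to Stream 2: Statistical methods, before analysis, for the four outcomes above:

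1. The prespecified 'other' contrast, and any pooled contrast of patients with and without mental illness, excludes patients with an eating-disorder code at or before the index date.
2. Those patients are reported as a separate row, numbers permitting.
3. The estimate including everyone is shown alongside.
4. Weight-based outcomes in the eating-disorder row are not interpreted as IBD severity.

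All other outcomes, and the make-up of the composite for them, stay as planned.

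**Cost.** Protocol wording and one group split. The plan must identify eating disorders for its composite in any case; the Read and SNOMED list under that heading in sTable 2.1 shows no entries in the available text, so it needs to be settled before the split is run. Precision for these outcomes falls in proportion to the eating-disorder share: a slight exclusion means the bias was probably slight, and a large one means it may have been worth removing. Some truly IBD-related low weight is lost from the main contrast, but the all-inclusive estimate still shows it.

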The Optimum Patient Care Research Database (OPCRD). This database incorporates pseudonymised primary care records from 700 GP practices distributed across England, Wales, Scotland and Northern Ireland. The current OPCRD cohort size is over 5 million actively registered people, and historic records available for 10.1 million people. The cohort dataset can be enhanced through direct-to-patient and direct-to-care provider questionnaires at additional cost if required.

Study design

The proposed study will use the retrospectively collected data of all eligible patients within the database at the date of data extraction. Within this primary care cohort, all patients with IBD comprising of the three main subtypes; ulcerative colitis (UC), Crohn's disease (CD) and IBD unclassified (IBDU), excluding microscopic colitis, radiation induced enterocolitis and drug-induced enterocolitis, will be identified using diagnostic codes and prescription records. A diagnostic algorithm will be developed to facilitate robust case identification of IBD and IBD subtypes, as well as mental health outcomes.

Statistical methods

We will use standard descriptive statistics (mean, standard deviations, etc) to describe the characteristics of the study cohort.

Recorded sociodemographic characteristics and clinical features

Sociodemographic data will comprise by age group, age at diagnosis, gender, ethnicity, and socioeconomic status. Ethnicity will be categorised as follows to be consistent with the UK official census categories: White, Asian, Black African/Caribbean, Mixed, and Other. The index of multiple deprivation (IMD) will be used as a measure of socioeconomic status. This is derived from patient postcode at the point of data extraction.

Stream 1: Study Cohort

Stream 1: Definition of people with new onset IBD

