We will use standard descriptive statistics (mean, standard deviations, etc) to describe the characteristics of the study cohort overall and by mental health phenotype. Across mental health condition phenotypes we will describe the incidence of recording of all the quality-of-life indicators, IBD severity markers, and healthcare resource utilisation outcomes up to five years after the index date (01/01/2015), compared to incidence in the group without mental health conditions. The end of follow-up will be the first of; 01/01/2020 (5 years after the index date) we will not follow patients up into 2020/21 due to changes in patient health behaviour and primary care interactions due to COVID-19, the patient's 25th birthday, date of loss to follow-up (either deregistration or death). All individuals contributing at least six months of follow-up time in the analysis will be included. We will not follow patients up into 2020/21 due to changes in patient health behaviour and primary care interactions due to COVID-19.

Relative incidence between those with and without mental health conditions will be estimated for repeated events (e.g. number of hospital admissions) and binary events (e.g. quality of life indicators) using, as appropriate, Poisson regression, negative binomial regression (if we need to account for overdispersion), or zero-inflated Poisson regression (if we need to model rare events). To account for variable duration of follow-up, we will include the natural logarithm of person-years of follow-up as a model offset. Confidence intervals will be estimated using robust SEs. Models will be adjusted for age, gender, socioeconomic status, ethnicity, and other childhood conditions (asthma, atopic dermatitis, allergic rhinitis, thyroid disease, epilepsy, diabetes, cancer, juvenile idiopathic arthritis (JIA) including systemic JIA, systemic lupus erythematosus (lupus), ankylosing spondylitis (AS) and psoriatic arthritis). Statistical significance for analyses will be reported using P values and 95% confidence intervals as appropriate.

Where numbers allow, we will report absolute and relative incidence in subgroups by, mental health condition group, age group (5-<12; 12-<16; 16-<18; 18-<25) (child, adolescent, young adult), and sex.

References

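### Stream 2 counts indicators recorded in GP records per person-year with no allowance for consultation frequency, so opportunistically coded items may be recorded more often in patients treated for mental illness

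*Combined protocol and SAP*

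**What the plan says.** The Data source section describes the database: "This database incorporates pseudonymised primary care records from 700 GP practices distributed across England, Wales, Scotland and Northern Ireland". It adds that questionnaires are possible ("The cohort dataset can be enhanced through direct-to-patient and direct-to-care provider questionnaires at additional cost if required"), but Stream 2 plans none.

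Under Stream 2: Statistical methods, "we will describe the incidence of recording of all the quality-of-life indicators, IBD severity markers, and healthcare resource utilisation outcomes" for up to five years after 01/01/2015. The models are Poisson, negative binomial or zero-inflated Poisson, with log person-years as the offset. They adjust for age, gender, socioeconomic status, ethnicity and a list of childhood conditions. Consultation frequency is neither a covariate nor the subject of a sensitivity analysis.

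Appendix 2, sTable 2.2 defines anxiety as "Any coded anxiety episode AND concurrent treatment for anxiety" and a depressive episode as "Any coded depressive episode AND concurrent treatment for depression". Recurrent depressive disorder can also be met by a code alone ("OR Any code for recurrent depressive disorder"). The components of the other-conditions phenotype that appear in sTable 2.3 need only a code.

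Under Stream 2: Study outcomes, "Hospital admissions will be separated into general admissions (including those for IBD) and psychiatric admissions". Primary care attendances, listed beside them, are not split. The only capture limitation stated there concerns medicines that primary care may not record well.

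Stream 1: Sensitivity analysis includes a check for bias from "people who are registered with GP practices but who do not attend their practice". Stream 2 has no counterpart.

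**The concern.** What is modelled is an entry in the record, not the state behind it. For a symptom, tiredness, a sleep problem, an absence or a low weight, an entry usually needs an occasion on which someone asks, measures and codes. A person-years offset equalises time under observation. It does not equalise the number of such occasions per year.

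The comparison is between patients partly selected for being in treatment and patients not so selected. If the first group consults more, it has more chances to acquire the code, even when the symptom is equally common in both groups.

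Quality of life is the primary objective of Stream 2, which is framed as the impact of mental health conditions. A ratio modestly above 1 for fatigue or abdominal pain would be read as impact when part of it may be observation. The protocol accepts that contact patterns matter: it ends follow-up at 01/01/2020 because patient behaviour and primary care interactions changed with COVID-19. It does not apply that reasoning to differences between the groups compared.

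**Working it through.** The documents give no contact rates, coding probabilities, sample size or expected effect, so there is no figure of the plan's to reproduce. What follows is an illustration with no true difference between the groups.

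**From the documents.** Follow-up is at most 5 years and at least 6 months. The listed end-of-follow-up events do not include the outcome itself, so a binary indicator is read as ever recorded during follow-up. sTable 2.2 is taken to define the Stream 2 anxiety and depression phenotypes, as it holds the only algorithms given.

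**Assumed.**
- c = 5 contacts a year in the comparator
- r = ratio of contact rates, exposed to comparator
- q = chance per contact that a state which is present gets coded
- s = share of the comparator's recording that is opportunistic

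**1. Binary indicators.** With equal true prevalence, prevalence cancels, and

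ratio = [1 − exp(−q·c·r·T)] / [1 − exp(−q·c·T)].

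At T = 5, the comparator has 25 contacts:

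| q | Recorded, comparator | r = 1.5: recorded, ratio | r = 2: recorded, ratio |
|---|---|---|---|
| 0.01 | 22.1% | 31.3%, 1.41 | 39.3%, 1.78 |
| 0.05 | 71.3% | 84.7%, 1.19 | 91.8%, 1.29 |
| 0.2 | 99.3% | 99.9%, 1.01 | 100.0%, 1.01 |

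For example, at q = 0.01 and r = 2: (1 − e^−0.50)/(1 − e^−0.25) = 0.393/0.221 = 1.78. Percentages are of patients who have the state.

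Short follow-up leaves more room for bias. At T = 0.5 and r = 2 the ratios are 1.98, 1.88, 1.61 and 1.29 for q = 0.01, 0.05, 0.2 and 0.5.

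**2. Repeated recordings.** Rate ratio = 1 + s(r − 1).
- r = 1.5: 1.125, 1.25 and 1.50 for s = 0.25, 0.5 and 1.
- r = 2: 1.25, 1.50 and 2.00 for the same s.
- s = 0, where recording is driven entirely by symptoms: 1.00 whatever r is.

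**3. Could such a ratio reach nominal significance?** Upper-tail chance = Φ(ln RR / √(1/e₁ + 1/e₂) − 1.96), where e₁ and e₂ are the expected numbers recorded in the comparator and exposed groups.

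Assume N = 1000, 21.6% exposed (borrowed from the prevalence in the US study cited in Background) and a recorded risk of 20% in the comparator. At RR 1.25, e₁ = 784 × 0.20 = 156.8 and e₂ = 216 × 0.20 × 1.25 = 54.0. Then 0.223/0.158 = 1.41, and Φ(1.41 − 1.96) = 29%. At RR 1.50 the chance is 78%. With N = 500, 15% exposed and a 10% risk, the chances are 9% and 23%.

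**4. Attendances.** No recording model is needed. A mental health review is an attendance and counts towards the ratio. Admissions have a psychiatric category that allows the two kinds of use to be separated; attendances have none.

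**The case against.** Several stronger readings are tempting, and the documents do not support them.

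- **That every Stream 2 indicator depends on a GP contact.** Prescriptions, supplements, surgery, stoma and admissions need an entry in the GP record, but nothing says that the entry must arise at a consultation.
- **That exposure produces contacts by definition.** Treatment is required for anxiety, depressive episode and one branch of recurrent depression, not throughout. Groups are fixed at the index date and outcomes are counted afterwards, and counselling or CBT is not said to take place at the practice. More contacts during follow-up are likely, not definitional.
- **That a higher attendance ratio is an artefact.** Attendances are a declared resource-use outcome, and extra visits are real use. Only the interpretation is limited.
- **That unmeasured patients will be counted as not underweight.** The protocol states neither a denominator nor a rule for missing weights.

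Two further objections have force. The Stream 1 check concerns controls without IBD who may never attend. Both Stream 2 groups have IBD identified from diagnostic codes and prescription records, so complete non-attendance is less of a problem and the missing counterpart is not a plain inconsistency. And the illustration lets an extra mental health contact yield a symptom code as readily as any other contact. Where coding follows symptoms alone, there is no bias.

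What survives is that consultation frequency can differ between two groups that both attend, and that nothing planned would show whether it matters.

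**Conclusion.** The point holds for opportunistically coded indicators: IBD symptoms, tiredness, sleep problems, school or work absence, and underweight. Their recording may be higher in the anxiety and depression groups without a true difference, and the person-years offset and adjustment set do not address this. Neither the existence nor the size of the bias can be established from the documents. At twice the contacts over five years, the assumed inputs give a ratio from about 1.0 to about 1.8; it can be higher with short follow-up and is smaller with a smaller contact difference. A reader might infer that the Stream 2 associations would be wholly an artefact of observation, but nothing in the documents shows that. For attendances, the defect is that mental health reviews cannot be separated from other use. This is an inexpensive improvement that should be made, because it changes how far the quality-of-life and resource-use ratios can be interpreted.

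**What to change.** 1. Report primary care attendances split into mental-health-coded and other, alongside the total.
2. For the opportunistically coded indicators, pre-specify a sensitivity analysis that adds the number of primary care consultations in the 12 months before 01/01/2015 to the model, and repeat it in patients with at least one such consultation. Keep the planned model as primary. Describe an indicator whose ratio moves materially towards 1 as possibly due to ascertainment.
3. Report the proportion with weight and height recorded in each group, and give underweight among those measured as a supplementary result.

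The cost is mainly programming. Attendances are already an outcome, and the Stream 1 check already uses consultations before an index date. The documents do not confirm that attendances carry a usable reason code, so that should be verified first.

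The drawbacks are why these remain sensitivity or supplementary analyses. Earlier consultations partly reflect mental illness and IBD severity, so adjustment may over-correct. Pre-index counts may miss some of the difference in contacts during follow-up, but adjusting for post-index contacts could remove part of a real effect. Restricting underweight to measured patients may add selection.
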